## SUMMARY

Introduction. Vitamin D regulates mineral metabolism, playing a crucial role in maintaining adequate bone density. Immunomodulatory, cardioprotective and

Version December 7th, 2015

antiproliferative effects have been described recently. Its deficiency has been associated with diabetes, cancer and increased mortality. 25OH vitamin D (25VD) is stable (with a half-life of over 2 weeks) and suitable for the evaluation of vitamin D sufficiency. It has been found that levels of 25VD are inversely related to those of the parathyroid hormone (iPTH), and its supplementation has been associated with a decrease in levels of iPTH in patients with Chronic Kidney Disease, although these results have not been uniform in patients on hemodialysis (HD). The usual treatment for secondary hyperparathyroidism in HD with active and analogous forms of vitamin D increases the risk of hyperphosphatemia and vascular calcifications.

The aim of the study is to evaluate whether cholecalciferol supplementation for a period of 12 weeks can normalize decreased levels of 25VD and reduce increased iPTH in HD patients with a vitamin D deficiency. Secondary aims: to evaluate decrease in inflammation, anemia or use of erythropoietin (epo).

**Design.** Randomized, double blind clinical trial in two arms of HD patients with 25VD deficiency and secondary hyperparathyroidism, one arm to be treated with cholecalciferol supplementation and the other with a placebo, for a period of 12 weeks.

**Population.** Patients over 18 years of age on HD for more than 3 months and levels of 25VD < 30 ng / ml and iPTH >300 ng/ml , who sign a consent form. Patients will be recruited over a period of one year. Once their consent has been obtained, iPTH and 25VD levels will be measured. Randomization will be achieved by using a table of random numbers at the pharmacy, and neither doctors nor patients will know which group they have been assigned to.

Treatment. Supplementation will consist of one 5000 IU 25VD tablet or placebo during dialysis for a period of 12 weeks.

Monthly monitoring will include: hemoglobin (g/dl), Calcium (mg/dl), Phosphorous (mg/dl), iPTH (ng/ml), epo dose (IU/kg/week), epo resistance (IU/kg/week/g Hb).

At the beginning and end of the study the following will be measured: alkaline Phosphatase (IU/ml), PCR (mg/L), 25VD (ng/ml), ferritin (ng/ml) and transferrin saturation, quality of life (SF36).

During the study, doses of calcitriol or paricalcitol will not be modified.

The study will be discontinued if calcemia  $\geq$  10.5 mg/dL is detected on two occasions.

Size of sample is estimated at 120 patients for a iPTH decrease of 20% in 35% of patients in group treated (assuming 15% follow-up losses). Analysis will be done for Intention to treat for the primary outcome.

Ethical aspects: Authorization has been obtained from the Ethics Committee of the institution as regards Good Clinical Practices, Helsinki Declaration and national regulations. The test will be registered with Cochrane and the Ministry of Public Health.

## INTRODUCTION

Vitamin D regulates the metabolism of calcium and phosphorous and plays a crucial role in maintaining adequate bone density. Apart from mineral

metabolism, immunomodulatory, cardioprotective and antiproliferative effects of vitamin D (1,2) have been described recently.

Studies in the general population have found a correlation between deficiency of 25OH vitamin D (25VD) and mortality and morbidity (3). Said correlation was also confirmed in patients with end stage renal disease treated with hemodialysis and peritoneal dialysis (4, 5, 6). 25VD is very stable and has a lengthy half-life (close to 2 weeks) which makes it the optimum metabolite for the measurement and evaluation of vitamin D sufficiency (7).

The synthesis of the active form of vitamin D3 (1,25 (OH) 2 D3) or calcitriol is carried out by means of a second hydroxylation mediated by 1 $\alpha$  hydroxylase produced in the proximal tubule of the kidney. The presence of cells that contain 1 $\alpha$  hydroxylase capable of synthesizing calcitriol in non-renal sites is significant as renal function deteriorates, but adequate levels of 25VD in the blood are also required (8).

Normal levels of 25VD are considered to be those above 30 ng/ml, moderate deficiency or insufficiency when levels are between 10 and 30 ng/ml, while severe deficiency is when concentration is below 10 ng/ml (9).

It has been found that levels of 25VD are inversely related to those of parathyroid hormone (iPTH) (10), and its supplementation has been associated with a decrease in levels of iPTH in patients with Chronic Kidney Disease (CKD), especially in those with a glomerular filtration rate (GFR) higher than 30 ml/min.

The reported results for patients on dialysis have been less consistent. Some studies have reported a decrease in iPTH levels after 25VD supplementation in patients on dialysis as well.

Among the effects of vitamin D not related to mineral and bone metabolism we can find those related to inflammation, angiotensin renin system, arterial pressure and cancer (11). Some studies suggest that it could be through inflammation that 25VD might influence erythropoiesis, thus explaining the association reported in recent observational studies (12, 13). It has been reported that the decrease of 25VD and the higher levels of C reactive protein (CRP) were associated independently with less hemoglobin in individuals with kidney disease not requiring dialysis (14, 15, 16, 17), and that higher doses of erythropoietin are needed in patients on dialysis.

For decades secondary hyperparathyroidism has been treated with active forms of vitamin D (calcitriol) and analogous forms of vitamin D (paricalcitol) (8,9).

The use of calcitriol is associated with a risk of phosphorous increase and of vascular calcifications. While these effects are less significant with paricalcitol, the cost is several times higher which makes it unaffordable for many countries and many patients.

There are not enough randomized clinical trials that confirm the possibility of treating secondary hyperparathyroidism with cholecalciferol (28-31). This is a drug with minor side effects and low cost so it would be very advantageous for all patients, both in developing and developed countries.

## AIMS

The aim of the study is to evaluate whether cholecalciferol supplementation for a period of 12 weeks can normalize decreased levels of 25VD and reduce increased iPTH in HD patients with a vitamin D deficiency. A secondary aim is to

evaluate whether this treatment will reduce anemia or the need for erythropoietin in this population.

### Specific Aims

1. Primary aim: to analyze whether it is possible to normalize levels of 25VD and reduce high levels of iPTH
2. Secondary aim: to evaluate whether it is possible to improve renal anemia in hemodialysis patients with a 12-week course of cholecalciferol
3. Secondary aim: to investigate whether cholecalciferol supplementation in HD patients is associated with hypercalcemia and hyperphosphatemia

### METHODS

Design. Randomized, double blind clinical trial in two arms of chronic HD patients with vitamin D deficiency and secondary hyperparathyroidism, one arm to be treated with cholecalciferol supplementation and the other with a placebo, for a period of 12 weeks.

### POPULATION

Criteria for inclusion: Age 18 or over, signed informed consent form, CKD with regular dialysis treatment for at least 3 months, levels of 25VD < 30 ng / ml and iPTH >300 ng/ml, stable doses of calcitriol or paricalcitol over the last 30 days.

Criteria for exclusion: Congestive heart failure class III or IV or unstable angina

or myocardial infarction or stroke during the previous 3 months, active malignant neoplasm, use of any trial medication, life expectancy lower than 6 months, corrected calcemia  $\geq 10.5$  in the 2 months prior to recruitment, intake of cholecalciferol or ergocalciferol in the 2 months prior to recruitment, prospective move to another city or transfer to PD in the following 6 months.

Patient recruitment. Patients will be recruited over a one-year period when the study will be explained to them, and samples will be taken to assess whether they fulfill the criteria for inclusion in the trial. Once iPTH and 25VD testing has taken place, eligible participants will be requested to sign an informed consent form, and will be told that they will be treated either with cholecalciferol or a placebo. They will be assigned to one of the arms using a table of random numbers at the pharmacy of the institution, stratified in two subgroups according to vitamin D levels: below 15 ng/ml or between 15 and 29.

Randomization. Once approval has been received from the Ethics in Research Committee and the consent form has been signed, patients will be assigned to one arm by using a table of random numbers, according to a number from 0 to 9 which will be drawn at random at the time the patient is included. For purposes of randomization, one fixed number will be skipped from the starting point which is only known by the person who does the randomization at the pharmacy, using a starting point selected initially on the table. Notification of the arm allocated will arrive in sealed envelopes with the medication to be taken (either cholecalciferol or the placebo) which will be administered orally during dialysis.

The laboratory that prepares the medication and the placebo will send them to the pharmacy labelled as medication A and B. Then the pharmacy of the

institution will send the tablets to the patient, neither the doctors nor the patient knowing what arm he has been assigned to. The medication will be administered by the nurse during dialysis.

It will not be necessary to make changes to the dietary intake of vitamin D as dairy products, which are the main source of dietary vitamin D, are strictly limited in the diets of these patients.

Treatment: Supplementation will consist of one 5000 IU tablet of 25VD or placebo taken during dialysis for a period of 12 weeks. A nurse from the team will ensure access to the medication by being in permanent contact with the pharmacy. Monthly follow-up of the patients in the study will include evaluation of laboratory tests as well as normal clinical controls during dialysis (weight, arterial pressure and intra-dialysis hypotension events), and monthly report of dosage of erythropoietin (IU/kg/week) for the calculation of the index of resistance to erythropoietin (IU/kg/week / g of Hb).

Laboratory testing to be done monthly will include: hemoglobin (g/dl), Calcium (mg/dl), Phosphorous (mg/dl), and iPTH (ng/ml). At the beginning and at the end of the study the following will be measured: Alkaline Phosphatase (IU/ml), CRP (mg/L), ferritin (ng/ml), transferrin saturation, and 25VD (ng/ml).

The measuring of hemoglobin will be done by Siemens Healthcare Diagnostics' Advia 2120 haematological analyzer using the cyanmethemoglobin method modified without cyanide, with Siemens controls and calibrators. Dosing of vitamin D, iPTH and ferritin will be done by Siemens Healthcare Diagnostics' Advia Centaur XP analyzer using the chemiluminescence method, with BIORAD controls and Siemens calibrators.

Other measures will be taken as follows: for calcium, by the Arsenazo III endpoint method, for phosphorous, by the UV phosphomolibdate method, for alkaline phosphatase, by the kinetic technique of paranitrophenol phosphate, for iron, by the endpoint ferrocin method, for transferrin, by the immunoturbidimetric method maximized with PEG, and for reactive C Protein, by the immunoturbidimetric method maximized with latex. All of these will be done by Siemens Healthcare Diagnostics's Advia Chemistry 1800 autoanalyzer with BIORAD controls and Siemens calibrators.

Both prior to the start of the study and after it has ended, quality of life will be evaluated using SF36 auto-administered protocol.

During the 12 weeks of the study, doses of calcitriol or paracalcitol must not be modified. The study will be discontinued in those patients who present levels of calcemia  $\geq 10.5$  mg/dL on two occasions.

Operational Definitions: 25VD levels are considered normal when above or equal to 30 ng/ml, and severe deficiency (SD-25VD) when below 10 ng/ml. Anemia is defined as presenting levels of Hb below 10g/dl or the need for epo. It is classified as mild anemia when patients have no anemia or require doses of epo below or equal to 2000 IU per week, and, failing this, very mild anemia. Ferritin is considered to be high when over 500 ng/ml. Measurements of all analytes will be done with Siemens equipment at the CASMU laboratory.

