#### Calculation of sample size

It was estimated, by using free access epidemiological calculator Open Epi (to be found at <http://www.openepi.com/v37/SampleSize/SSCohort.htm>), that necessary sample size to show a IPTH decrease of 20% in 35% of patients in the group treated (information we found in a previous observational study) is 102, and assuming a 15% loss of follow-up, a sample size of 120 was decided on. This size is more demanding than the 50 patients needed to demonstrate the correction of 25VD in 50% of patients.

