#### Expected Results

Primary end point: A difference in the percentage of patients normalizing levels of 25VD of at least 45% of the group treated vs placebo.

Percentage of patients of at least 30% in the group treated vs placebo presenting a decrease of 20% from previous levels of IPTH.

Secondary end point: Percentage of patients with an increase in Hb or a decrease in resistance to erythropoietin

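### The iPTH inclusion threshold carries a unit (ng/ml) that, read literally, would exclude every patient; the unit needs checking and correcting, while the end point and sample size are unaffected

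*Protocol*

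**What the plan says.** The criteria for inclusion in the Population section of the protocol ask for "levels of 25VD < 30 ng / ml and iPTH >300 ng/ml". The Population paragraph of the Summary has the same rule: "levels of 25VD < 30 ng / ml and iPTH >300 ng/ml , who sign a consent form".

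The unit recurs where iPTH is listed for monthly measurement. The Summary has "Phosphorous (mg/dl), iPTH (ng/ml), epo dose (IU/kg/week", and the laboratory list in the Population section has "hemoglobin (g/dl), Calcium (mg/dl), Phosphorous (mg/dl), and iPTH (ng/ml". The unit therefore appears four times and is the same each time.

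On the assay, the protocol says only: "Dosing of vitamin D, iPTH and ferritin will be done by Siemens Healthcare Diagnostics' Advia Centaur XP analyzer". It names the instrument and method but neither a reporting unit nor a reference range for iPTH. The Operational Definitions paragraph sets cut-offs for 25VD, anemia and ferritin and none for iPTH. The inclusion criterion and its copy in the Summary are thus the only numeric definition of the hyperparathyroid population that the Design paragraph names.

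The iPTH end point under Expected Results counts patients "presenting a decrease of 20% from previous levels of IPTH". On the number of patients, the sample size section says that the size needed "is 102, and assuming a 15% loss of follow-up, a sample size of 120 was decided on".

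**The concern.** The figure selects the trial population. If its unit is wrong, the enrolment rule cannot be applied as written. Parathyroid hormone in blood is ordinarily expressed in picograms per ml, and a cut-off of 300 in nanograms per ml is 1000 times the same figure in picograms per ml. The protocol plans to recruit 120 patients in one year under a rule that, taken at face value, none of them would meet.

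What is at stake is auditability more than bias. Enrolment is checked against the written criterion, and a criterion that nobody meets turns every enrolled patient into a deviation on paper. A reader of the protocol also cannot tell from it alone which population was meant, because no other iPTH figure is printed to settle the matter. Carry-over from 25VD and ferritin, which are run on the same analyzer and are given in ng/ml, is a plausible origin, but that is inference.

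**Working it through.** **Inputs from the protocol**
- Inclusion threshold: iPTH above 300 ng/ml (Summary; Population, criteria for inclusion).
- Unit of the monthly iPTH measurement: ng/ml (Summary; Population, laboratory testing).
- iPTH end point: a fall of 20% relative to the previous level (Expected Results).
- Sample size: 102, raised to 120 for 15% losses (Calculation of sample size).

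**Input assumed, not in the protocol**
- iPTH in hemodialysis patients lies between about 300 and 5000 pg/ml. This is general knowledge of the measurement scale. It is set wide on purpose and varied below.

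**Step 1. The plan's own arithmetic.** The threshold is a stated figure with no derivation to reproduce. The allowance for losses does reproduce: 102 / (1 − 0.15) = 102 / 0.85 = 120. No calculation in the protocol uses the iPTH unit.

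**Step 2. Convert the threshold.** 1 ng/ml = 1000 pg/ml, so 300 ng/ml = 300 × 1000 = 300,000 pg/ml. Conversely, 300 pg/ml = 0.3 ng/ml.

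**Step 3. Compare it with the assumed range.** Ratio = 300,000 / patient value in pg/ml.

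| Patient iPTH, pg/ml | Same value, ng/ml | Written threshold / patient value | Above 300 ng/ml? |
|---|---|---|---|
| 300 | 0.3 | 1000 | no |
| 500 | 0.5 | 600 | no |
| 1000 | 1 | 300 | no |
| 2000 | 2 | 150 | no |
| 3000 | 3 | 100 | no |
| 5000 | 5 | 60 | no |

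No value in the range qualifies. The upper end of the assumption would have to be too low by more than a factor of 60 before any patient met the rule, so the result does not hinge on where in the range patients lie.

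**Step 4. Does the unit reach the end point?** Let x0 and x12 be a patient's levels at the start and at week 12, and let k be any conversion factor. The relative fall is (k·x0 − k·x12) / (k·x0) = (x0 − x12) / x0. The factor cancels, so a patient who falls by 20% in one unit falls by 20% in any other.

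**Step 5. Does the unit reach the sample size?** The 102 is built on the proportion of patients with that relative fall (35% in the treated group). By step 4 the proportion does not change with the unit label, so 102 and 120 stand as far as this point is concerned.

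**The case against.** The strongest case on the other side is that the protocol does not contradict itself here. It uses ng/ml for iPTH every time it prints a unit, and it gives no second unit, reference range or expected value that would expose a slip. This stands. The finding needs the picogram scale, which comes from outside the document, and that is why it is stated as an assumption with a range. Consistent repetition does not make the figure usable, however; it means that nothing elsewhere in the protocol corrects it.

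It is also fair to say that the 25VD cut-off of 30 ng/ml proves nothing by comparison. Different analytes need not share a scale, and the protocol's own ferritin cut-off of 500 ng/ml is likewise more than ten times the 25VD cut-off. No weight is put on that comparison.

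A further objection is practical. One named analyzer and one laboratory measure iPTH, so staff would most naturally compare the number on the laboratory report with 300 and recruit as intended. This too is largely right, and it limits the consequence.

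Three stronger readings are tempting, and the documents do not support them:
- A reader might infer that the trial could not recruit. That would require staff to convert results into ng/ml before applying the rule, and nothing in the protocol suggests they would.
- A reader might infer that the error damages the iPTH primary end point or the power. Both rest on a relative change, in which the unit cancels.
- A reader might infer that the wrong unit sits in the case report form. The form is cited as Annex 1 and is not shown, so this cannot be checked.

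**Conclusion.** The inclusion threshold is wrong as written, on the assumption that iPTH in these patients is on the picogram-per-ml scale (about 300 to 5000 pg/ml). On that range the written cut-off is 60 to 1000 times above patients' values. Read literally, no one would be eligible and every enrolled patient would count as a protocol deviation.

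This is a fault in the unit of an eligibility figure. It is not an error in the statistical calculations: randomization, end point, analysis and sample size do not depend on it, and its effect on recruitment is probably small. It deserves correction because it is the only numeric definition of the hyperparathyroid population and the protocol offers nothing to resolve it. Whether 300 is the appropriate clinical cut-off is not judged here.

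**What to change.** 1. Check which unit the named analyzer and laboratory report for iPTH.
2. Put that unit in place of ng/ml at all four places: the inclusion rule and the monthly monitoring list in the Summary, and the criteria for inclusion and the laboratory list in the Population section.
3. Have the sponsor confirm that the figure 300 was meant in that unit. If it was not, the sponsor must restate figure and unit together; this review proposes no value.
4. Check that the case report form (Annex 1, not shown) uses the same unit, and change it only if it does not.

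The cost is a wording correction in an amendment and, at most, a label change on the form. Sample size, end point and analysis stay as they are.

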### Statistics

Continuous variables with normal distribution will be compared using Student's test for independent or dependent samples as appropriate and will be presented as the mean  $\pm$  standard deviation. Categorical variables will be compared using Chi square test for paired or independent samples as appropriate

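### Randomisation is called stratified by 25VD, but the draw described uses no 25VD step and no restriction, so it is simple randomisation

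*Protocol*

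**What the plan says.** Three places in the Protocol describe the allocation.

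- **Population, Patient recruitment paragraph:** a random-number table at the pharmacy, "stratified in two subgroups according to vitamin D levels: below 15 ng/ml or between 15 and 29".
- **Population, Randomization paragraph:** the arm is chosen "according to a number from 0 to 9 which will be drawn at random at the time the patient is included". The table is read from a concealed starting point, and "one fixed number will be skipped from the starting point". The result travels in sealed envelopes with the medication.
- **Summary, Population paragraph:** "Randomization will be achieved by using a table of random numbers at the pharmacy". Strata are not mentioned.

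Eligibility requires "levels of 25VD < 30 ng / ml". Normalising 25VD is one of the two primary end points (Expected Results). The Statistics section says "Categorical variables will be compared using Chi square test for paired or independent samples as appropriate", with no mention of strata. The Protocol states no allocation ratio and no rule linking digits to arms.

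**The concern.** Stratification improves balance only if allocation is restricted inside each stratum, for example by permuted blocks. If each patient's arm is an independent draw, it makes no difference whether that draw comes from one table or from a separate table per stratum: the joint distribution of the allocations is the same. The concealed start and the fixed skip protect concealment and do nothing for balance.

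The Protocol therefore claims a design feature that its own procedure does not deliver. The factor was a sensible choice, because baseline 25VD is the starting value of the measure that defines a primary end point, reaching 30 ng/ml or more. Two things are at stake: chance imbalance in a likely predictor of that end point, and a trial report that would call the randomisation stratified when the written procedure has no such effect.

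A smaller point is that the upper stratum stops at 29 while eligibility runs to just under 30. If the laboratory reports decimals, a patient at 29.5 ng/ml is eligible but belongs to no stratum.

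**Working it through.** **Inputs from the Protocol.** Two arms. The sample size is 102, inflated for 15% loss: 102/0.85 = 120, as stated. For the 25VD end point, Calculation of sample size speaks of the number needed to "demonstrate the correction of 25VD in 50% of patients", and Expected Results asks for "A difference in the percentage of patients normalizing levels of 25VD of at least 45% of the group treated vs placebo". Together these imply about 50% − 45% = 5% normalising on placebo.

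**Assumptions, because the Protocol gives no figures.** 1:1 allocation; stratum sizes; the share q of patients below 15 ng/ml; the gap in response between strata.

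**1. Imbalance under the described draw.** Arm counts are Binomial(n, 0.5); two-sided tails:

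| Group | Event | Probability |
|---|---|---|
| All 120 | arms differ by 10 or more | 0.411 |
| All 120 | 70:50 or worse | 0.082 |
| Stratum of 30 | 60:40 or worse | 0.362 |
| Stratum of 40 | 60:40 or worse | 0.268 |
| Stratum of 60 | 60:40 or worse | 0.155 |
| Stratum of 90 | 60:40 or worse | 0.073 |

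Overall imbalance alone costs little. A 70:50 split has an effective size of 4 × 70 × 50/120 = 116.7, a loss of about 3%.

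**2. Difference between arms in the share of low-25VD patients.** SD = √(q(1−q) × 4/120). With q = 1/3 this is √(0.2222 × 0.0333) = 0.086, so the 95% range is ±1.96 × 0.086 = ±0.169. Simulation with blocks of 4 and 6 within each stratum gives an SD of 0.0125, a range of ±0.025.

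**3. Chance shift in the 25VD end point.** If the shares differ by d, each arm departs from the common share by d/2 in opposite directions. The treatment difference then moves by (d/2) × (treated-arm gap + placebo gap). Take a 30-point gap in the treated arm. With 5% normalising on placebo, the largest possible placebo gap is 0.05/(2/3) = 0.075.

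- Shift: (0.169/2) × (0.30 + 0.075) = 0.032, or ±3.2 points.
- If nobody normalises on placebo: (0.169/2) × 0.30 = 0.025, or ±2.5 points.
- With q = 0.2 and a 10-point gap: ±1.2 points. With q = 0.5 and a 40-point gap: ±4.5 points.

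The target difference is 45 points.

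**4. Test size and power, by simulation (20,000 runs per setting, N = 120, q = 1/3).** Size uses null rates of 10% and 40% by stratum in both arms. Power uses 35% v 15% with a 20-point stratum gap in both arms. CMH is the Cochran-Mantel-Haenszel test.

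| Draw | Test | Rejection under the null | Power |
|---|---|---|---|
| As described | chi-square | 5.0% | 72.5% |
| As described | CMH | – | 74.2% |
| Blocked in strata | chi-square | 4.0% (conservative) | 73.7% |
| Blocked in strata | CMH | 5.0% | 75.2% |

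Changing the draw alone adds about 1 point of power. Adjusting for stratum adds about 1.5 to 1.7 points.

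**The case against.** The strongest reply has four parts.

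**The paragraphs can be read together.** The recruitment and Randomization paragraphs are consecutive. The first announces strata and the second explains how the table is read, so two sequences, one per stratum, is a natural reading. Block details are also often kept out of a protocol to protect concealment. Withholding block sizes would indeed be fine, but this Protocol describes its draw and nowhere says that a restriction exists. Two unrestricted sequences are still simple randomisation, so this reading does not restore the stratification. The Summary's silence is, fairly, an abridgement and not a contradiction in itself.

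**The consequence is small.** This stands. At about 50% v 5% on the 25VD end point, with a 30-point stratum gap in the treated arm and 102 evaluable patients, simulated power exceeds 99.9% even with the described draw and an unadjusted chi-square. On the iPTH end point at an assumed 35% v 10% with a 10-point gap and 102 patients, power is 87.7% (described draw, chi-square) against 88.5% (blocked, CMH).

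**The 35% v 15% comparison rests on assumed inputs.** This also stands. The placebo rate is not in the Protocol, and that comparison uses all 120 patients without the 15% loss. A 10% placebo rate, with two-sided 5% alpha, 80% power and a continuity correction, reproduces the Protocol's 102. Most of the total power gain comes from adjustment, which could be had without changing the draw.

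**Stratum adjustment is a matter for the SAP, and the 15-to-29 gap depends on how results are reported.** Both are fair limits. Adjustment is asked for only if the SAP does not already provide it, and with whole-number results the gap vanishes.

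**Conclusion.** The concern holds and should be corrected, though it threatens no conclusion. The Protocol claims stratified allocation, the procedure it sets out is simple randomisation, and no other section supplies the missing restriction. There is no bias, and the planned chi-square keeps its size under the described draw.

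The loss is modest: a chance shift of about ±3 points on a 45-point target for 25VD normalisation (±1.2 to ±4.5 over the assumptions tried), and roughly 1 to 3 points of power on the iPTH end point for the draw and the adjustment together. These sizes rest on 1:1 allocation and on assumed stratum shares, stratum gaps and placebo rates. That the stratification has no effect as written rests on none of them.

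**What to change.** Have the pharmacy hold one allocation list per 25VD stratum, made with randomly permuted blocks of varying size (for example 4 and 6; another restricted method would also do). Say so in the Randomization paragraph and the Summary, and state the allocation ratio. The block sizes themselves can stay with the pharmacy.

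Write the strata as <15 and 15 to <30 ng/ml, so that every eligible value has a stratum however it is reported.

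Once allocation is blocked within strata, compare the primary end points adjusted for stratum, for example by Cochran-Mantel-Haenszel, unless the SAP already does so. The unadjusted chi-square would be slightly conservative.

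The cost is two lists and a few sentences, with N unchanged at 120. The one drawback is that blocks are slightly more predictable, which blinding, varying block sizes and pharmacy-held lists limit. If the sponsor prefers to keep the draw as it is, the claim of stratification should be removed.
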